### **Protocol Synopsis**

Title	A Randomized, Multicenter, Open Label Study Comparing the Omeza® Products Bundle to Standard of Care for Chronic Venous Leg Ulcers and Chronic Diabetic Foot Ulcers	
Sponsor	OMEZA, LLC	
Study No.	Protocol #100	
Study Site(s)	The study will be conducted in up to 3 clinical study sites in different regions of the United States	

#### Introduction:

Venous leg ulcers (VLU) and Diabetic Foot Ulcers (DFU) are common and complicated ulcers to treat [1], and result in high morbidity [2] and significantly reduced quality of life [3]. Normal wound healing consists of four overlapping phases: hemostasis, inflammation, proliferation, and remodelling [4]. Most ulcers heal when the cause is eliminated, and the ulcer is treated with standard wound care. Some ulcers, however, are for various reasons locked in the inflammatory stage and do not heal [5]. This study will compare the Omeza® Products Bundle to standard of care (SOC) in subjects with chronic venous leg ulcers and subjects with diabetic foot ulcers.

#### **Objectives**

#### **Primary**

 To compare the efficacy of Omeza® Products Bundle to standard of care in the treatment of chronic venous leg ulcers and diabetic foot ulcers.

#### Secondary

- To evaluate the safety profile of the Omeza® Products Bundle compared to standard of care in the treatment of chronic venous leg ulcers and diabetic foot ulcers.
- To obtain cost benefit data comparing the Omeza® Products Bundle compared to standard of care in the treatment of chronic venous leg ulcers and diabetic foot ulcers.

#### **Exploratory**

• To measure the Quality of Life (QoL) of the subjects with chronic venous leg ulcers and with diabetic foot ulcers.

#### Study Design

This is a randomized, multicenter, open-label study comparing the Omeza® Products Bundle versus standard of care treatments for 2 different types of chronic ulcers (venous leg ulcers and diabetic foot ulcers). The treatment period will be 12 weeks, with subjects coming into the study site weekly for evaluations, photography and formal measurements of the target wound, and dressing changes. There will be a total of 13 study site visits. The Screening Visit (Day 0) will occur 1 week prior to randomization and will include routine labs and vascular assessment to determine inclusion/exclusion of the potential subject from the study; followed by weekly treatment visits (Week 1 through Week 11); randomization will occur at Treatment Visit Week 1; the Treatment Visit Week 12/End of Study Visit will include end of study labs. Target wounds will be photographed and measured, and vascular assessment will be done at each of the 13 visits. Standard of care will be billed to subject's insurance for both TEST and SOC control.

If the wound closes before Week 12, the subject will continue to come in for all the remaining study visits until study completion. If the wound does not close by Week 12, the subject will be immediately exited from the study and no further follow-up will occur as part of the study.

#### **Kev Entry Criteria**

The target wound appears to be healthy vascularized tissue at time of placement of treatment product. The wound is free from clinical signs of infection or ischemic changes. Target wound does not have presence of local active soft tissue infection.

- No known allergy to the study treatment or SOC materials or components of the multi-layer compression bandaging, or who cannot tolerate multi-layer compression therapy
- Presence of any condition(s) which seriously compromises the subject's ability to complete this study or has a known history of poor adherence with medical treatment.

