#### Eligibility Criteria Venous Leg Ulcer (VLU):

#### Inclusion Criteria:

- 1. Male or female 21-80 years of age
- 2. Participated in the informed consent process and signed study specific informed consent document
- Willing and able to comply with study procedures, including study visits and study dressing regimens
- 4. Confirmation of venous disease by non-invasive venous studies with either Doppler-confirmed venous reflux or having ≥ 2 clinical characteristics of venous insufficiency (varicose veins, lipodermatosclersosis, venous dermatitis, atrophie blanche, edema). Biopsy done to exclude other skin conditions e.g. cancer on ulcers ≥ 6 months
- 5. HbA1c of ≤ 10%
- 6. Have a venous ulcer between the knee and ankle, at or above the malleolus
- 7. Target wound size  $\geq 4 \text{ cm}^2$  to  $\leq 150 \text{ cm}^2$  in area without exposed tendon, muscle or bone
- 8. Target wound duration of at least 3 months and less than or equal to 12 months as of the date the subject signs consent for study
- 9. VLU may have characteristics that include yellow/white slough with or without fibrous/scar tissue and/or non-viable tissue, but not mandatory
- 10. Be willing and able (or have family member/friend willing and able) to apply required dressing changes as well as the ability of the subject to tolerate limb compression bandage

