### 3 Study Design

### 3.1 Description of the Study Design

This is a randomized, multicenter, open-label study comparing the Omeza® Products Bundle versus standard of care treatments for 2 different types of chronic ulcers (venous leg ulcers and diabetic foot ulcers). The treatment period will be 12 weeks, with subjects coming into the study site weekly for evaluations, photography and formal measurements of the target wound, and dressing changes. There will be a total of 13 study site visits. The Screening Visit (Day 0) will occur 1 week prior to randomization and will include routine labs and vascular assessment to determine inclusion/exclusion of the potential subject from the study; followed by weekly treatment visits (Week 1 through Week 11); randomization will occur at Treatment Visit Week 1; the Treatment Visit Week 12/End of Study Visit will include end of study labs. Target wounds will be photographed and measured, and vascular assessment will be done at each of the 13 visits. Standard of care will be billed to subject's insurance for both TEST and SOC.

If the wound closes before Week 12, the subject will continue to come in for all the remaining study visits until study completion. If the wound does not close by Week 12, the subject will be immediately exited from the study and no further follow-up will occur as part of the study.

Table 1: Study Plan

Study Period	Visit	Purpose
Screening	Screening (Day 0)	Determine eligibility, routine labs,
		vascular assessment, photos and
		measures
Baseline /	Treatment Visit Week 1	Review eligibility, randomization,
Randomization		Wound-QoL questionnaire, vascular
		assessment, photos and measures,
		begin study treatments.
Treatment	Treatment Visits Week 2 - Week	Study treatments, vascular assessment,
	11	photos and measures
End of Study Visit	Treatment Visit Week 12	End of Study routine labs, vascular
		assessment, photos and measures,
		Wound-QoL questionnaire

For subject to be eligible they must meet entry criteria. If the subject is not found eligible at Treatment Visit Week 1, the subject may be re-screened once or may be replaced.

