#### 4.3.2 Randomization Scheme

It will be determined if a subject is eligible to participate in the study at Treatment Visit Week 1, and the subject will be randomized 2:1 to Omeza® Products Bundle or SOC. Randomization numbers will be generated in blocks and consist of the 2-digit site number, followed by a 4-digit subject number. Randomization numbers will be assigned consecutively to each subject in the order in which they become eligible for randomization. Since this is an open label study, a randomization schedule indicating if the subject is assigned to TEST or SOC will be provided to each study site.

The subject will keep this unique randomization number for the duration of the study. Once a subject is randomized, the randomization number will be the identifying number for that subject.

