#### 6.2 Treatment Visit Week 1/Randomization/Baseline

Subjects will return for review of eligibility, baseline assessments, randomization and initiation of assigned treatment:

- Review of inclusion/exclusion criteria
- Subject to complete Baseline Wound-QoL questionnaire
- Concomitant medications
- Adverse event monitoring
- Wound examination
- Vascular assessment
- Target wound measurement and photography
- Randomization
- Wound Care, including the application of treatment (either TEST or SOC depending on randomization assignment see Appendices 2-4 for method)
- Schedule Treatment Visit Week 2

#### 6.3 Treatment Visits Week 2 - Week 11

Subjects will return to the study site once a week for a total of 11 Treatment Visits. These visits will include wound care and follow-up assessments. Every attempt will be made to schedule each Treatment Visit within the study day window of 7 days +/- 1 day, to assure proper wound care.

- Concomitant medications
- Adverse event monitoring
- Wound examination
- Vascular assessment
- Target wound measurement and photography
- Wound Care, including the application of treatment (either TEST or SOC depending as randomization assignment)
- Schedule the next weekly treatment visit

Note: If the wound closes before Week 12, the subject will continue to come in for all the remaining study visits until study completion, but the TEST subjects will be treated with the Omeza® Skin Protectant only.

### 6.4 End of Study Visit/ Treatment Visit Week 12

Subjects will return to the study site for the End of Study Visit on Week 12. If the wound has not closed by Week 12, the subject will be immediately excited from the study and no further follow-up will occur as part of the study.

- Routine laboratory evaluations
- Subject to complete end of Study Wound-QoL questionnaire
- Concomitant medications
- Adverse event monitoring
- Wound examination
- Vascular assessment
- Target wound measurement and photography
- Wound Care, including the application of treatment (either TEST or SOC depending on randomization assignment)

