## 9.8 Replacement of a Subject Who Discontinues Study Treatment

Subjects who met entry criteria and have been randomized will not be replaced if they drop out from the study for any reason.

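### The synopsis times a wound-bed entry criterion to product placement, after open-label randomization, and the re-screening and replacement rules do not clearly exclude subjects already randomized

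*Protocol*

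**What the plan says.** The synopsis, under Key Entry Criteria, requires: "The target wound appears to be healthy vascularized tissue at time of placement of treatment product". The full VLU and DFU eligibility lists, in the synopsis and again in Section 4.2, do not contain this condition. The nearest items there exclude gangrene or infection of the study ulcer.

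Three places put eligibility before allocation:
- Section 4.3.2: "It will be determined if a subject is eligible to participate in the study at Treatment Visit Week 1", after which the subject is randomized 2:1.
- Section 6.2, which describes the visit thus: "Subjects will return for review of eligibility, baseline assessments, randomization and initiation of assigned treatment". Its list opens with "Review of inclusion/exclusion criteria", reaches randomization later, and only then gives "Wound Care, including the application of treatment (either TEST or SOC depending on randomization assignment see Appendices 2-4 for method".
- Table 1 in Section 3.1, which has the eligibility review first, then randomization, with the start of treatment last.

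Two rules govern what happens to a subject who fails. Section 3.1: "If the subject is not found eligible at Treatment Visit Week 1, the subject may be re-screened once or may be replaced". Section 9.8: "Subjects who met entry criteria and have been randomized will not be replaced if they drop out from the study for any reason".

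Section 4.3.2 also says that the trial is open label and that each site is given the schedule showing which arm each subject is assigned to. Section 10.1 defines the ITT population as randomized subjects with at least one study treatment and at least one post-baseline measurement.

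**The concern.** Whether a wound bed looks healthy is a matter of judgement. Timed as the synopsis times it, that judgement falls after the investigator knows the arm. If a subject can then be declared ineligible and re-screened or replaced, the randomized comparison is open to selection made with knowledge of the allocation. Wound-bed appearance is plausibly related to healing, so this selection could bear on the primary endpoint. The other rules matter because they decide whether the slip in timing stays a drafting inconsistency or also gives a route out of the trial after randomization.

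**Working it through.** The plan gives no figure on this point, so the check is mainly a comparison of sections.

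1. **When the criterion is judged.** The synopsis ties it to placement of the product. In Section 6.2, application of treatment is listed after randomization and depends on the assigned arm. In Appendices 2 to 4 the primary dressing is step 4 in every procedure. In TEST it follows lavage, debridement as indicated and a second lavage. In SOC it follows topical anesthetic, debridement as indicated and saline. Read literally, the criterion is judged after the arm is known and after arm-specific wound preparation.

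2. **When eligibility is settled elsewhere.** Section 4.3.2, the Section 6.2 list and Table 1 all settle it before randomization. A condition defined at a later event cannot be confirmed at an earlier review, so the synopsis and these sections cannot both be followed.

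3. **Whether the criterion is operative.** A site working from the Section 4.2 lists would not apply it. A site working from the synopsis would. The protocol does not say which governs.

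4. **What follows if a subject fails at placement.** The Week 1 visit contains the eligibility review, randomization and first treatment. The Section 3.1 rule refers to that visit as a whole and sets no cut-off at randomization. Section 9.8 has two conditions, having met entry criteria and having been randomized. A subject said to fail a criterion at placement satisfies only the second. Section 9.8 also does not mention re-screening.

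5. **Analysis set.** A subject removed at Week 1 may have no post-baseline measurement and would then be outside the ITT population of Section 10.1. This is possible, not certain: Sections 4.3.3, 6.5 and 9.7 ask for End of Study evaluations after early withdrawal.

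6. **Knowledge of the arm.** The site holds the open schedule and numbers are assigned consecutively. The next assignment can therefore be known even before the eligibility review, and moving the criterion earlier in the visit would not by itself remove the exposure.

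7. **Size.** Inputs from the protocol: 78 subjects randomized 2:1 (52 TEST, 26 SOC), SD 20, target difference 14, two-sided 5% level.
   - SE = 20 × √(1/52 + 1/26) = 4.80. As a check on these inputs, 14/4.80 = 2.91 and Φ(2.91 − 1.96) gives 83.0% power (82.1% with the t distribution), which agrees with the stated figure of over 80% in Section 10.4.
   - If the worst-looking fraction q of an arm is removed, and appearance correlates ρ with the outcome, that arm's mean shifts by ρ × 20 × φ(z_q)/(1 − q). The bias in the treatment difference is the TEST shift minus the SOC shift.
   - With q = 0 in both arms the bias is 0. With equal q and equal ρ in both arms the two shifts cancel. The documents give neither q nor ρ for either arm, so no value can be derived from them.

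**The case against.** The strongest reply is that the operative text is clear. Sections 4.3.2 and 6.2 and Table 1 all put eligibility first. The synopsis paragraph is a loose summary that mixes inclusion and exclusion wording, and its wound-bed condition is in none of the full lists. The Section 3.1 sentence follows a statement that subjects must meet entry criteria, so it reads naturally as the review before randomization. If eligibility is a precondition of randomization, Section 9.8 covers every properly randomized subject. As an account of what was probably intended, this stands. It does not remove the contradiction, and the literal wording of Sections 3.1 and 9.8 still leaves the gap.

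Several stronger readings are tempting but not supported:
- **That randomized subjects will be re-screened or replaced.** No section says so.
- **That the criterion conflicts with VLU inclusion 9**, "VLU may have characteristics that include yellow/white slough with or without fibrous/scar tissue and/or non-viable tissue, but not mandatory". Debridement as indicated precedes the primary dressing in both arms, so slough at enrolment and healthy tissue at placement are compatible.
- **That a removed subject also leaves the Safety Population.** The lavage is one of the three bundle products (Section 5.1) and is applied before the collagen matrix, so a TEST subject stopped at placement of the matrix has arguably received study treatment.
- **That the criterion applies only to TEST.** Section 6.2 uses the word treatment for both arms.
- **That the type I error is inflated by a known amount.** Removing 2% to 10% of TEST subjects and no SOC subjects, with correlations of 0.3 to 0.5, would shift the difference by 0.3 to 1.95 units and give a two-sided error of 5.0% to 6.9%. Every one of those inputs, including removal from one arm only, is an assumption from outside the documents.

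**Conclusion.** The concern holds as a contradiction combined with an incomplete safeguard. The synopsis places a subjective entry judgement after open-label allocation, against Sections 4.3.2 and 6.2 and Table 1. Sections 3.1 and 9.8, as worded, do not rule out re-screening or replacing a subject who fails it then. The protocol permits this without directing it. The conclusion rests on reading the timing phrase and the two replacement rules literally. Any bias would be zero with no removals and small with similar removal in both arms; beyond that, the documents do not allow a size to be stated. The correction is worth making because it is nearly free and closes a route to exclusion after randomization.

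**What to change.** Four changes to the protocol:

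1. Reconcile the synopsis Key Entry Criteria with Sections 4.2, 4.3.2 and 6.2 so that no entry criterion is judged after randomization. Whether and how the wound-bed condition is kept is for the clinical team.
2. In Sections 4.3.2 and 6.2, require all eligibility to be recorded as final before the subject's next assignment on the site-held schedule is consulted. This is needed because an earlier time for the criterion does not help if the arm is already known.
3. In Section 3.1, limit re-screening and replacement to subjects not yet randomized.
4. In Section 9.8, state that no randomized subject is replaced or re-screened for any reason, including ineligibility found later.

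Changes 1, 3 and 4 are wording only. Change 2 adds a short record at the Week 1 visit and depends on site discipline, since the schedule remains at the site. None adds a visit or an assessment.

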#### **Treatments**

#### **STANDARD OF CARE:**

#### Venous Leg Ulcer

- 1) Apply topical anesthetic
- 2) Perform appropriate sharp debridement as indicated
- 3) Clean wound with saline
- 4) Apply collagen alginate as primary dressing
- 5) Apply foam as secondary dressing
- 6) Soft roll and compressive wrap (Dynaflex™ or Profore or any other preferred multi-layer compression bandage system)

#### Diabetic Foot Ulcer

- 1) Apply topical anesthetic
- 2) Perform appropriate sharp debridement as indicated
- 3) Clean wound with saline
- 4) Apply collagen alginate as primary dressing
- 5) Apply foam as secondary dressing
- 6) Offloading of the DFU using standard of care practices at the clinical study site

#### TEST/ OMEZA® PRODUCTS BUNDLE:

#### Venous Leg Ulcer

- 1) Apply Omeza® Lidocaine Lavage and after 5 minutes wipe out debris
- 2) Perform appropriate sharp debridement as indicated
- 3) Apply additional Omeza® Lidocaine Lavage and wipe out debris
- 4) Apply Omeza® Collagen Matrix as primary dressing
- 5) Apply Omeza® Skin Protectant on periwound and surrounding intact skin from knee to toes
- 6) Apply foam as secondary dressing
- 7) Soft roll and compressive wrap (Dynaflex™ or Profore or any other preferred multi-layer compression bandage system)

#### Diabetic Foot Ulcer

- 1) Apply Omeza® Lidocaine Lavage and after 5 minutes wipe out debris
- 2) Perform appropriate sharp debridement as indicated
- 3) Apply additional Omeza® Lidocaine Lavage and wipe out debris
- 4) Apply Omeza® Collagen Matrix as primary dressing
- 5) Apply Omeza® Skin Protectant on periwound and surrounding intact skin from knee to toes
- 6) Apply foam as secondary dressing
- 7) Offloading of the diabetic foot ulcer using standard of care practices at the clinical study site

#### **Number of Subjects and Population**

Sample Size: Approximately 78 randomized at 2:1 ratio (39/indication, with 26 TEST/13 SOC for each

#### indication).

Subjects who are diagnosed with one of the following chronic ulcers and who meet the entry criteria will be randomized into the study: 1) venous leg ulcer or 2) diabetic foot ulcer

Each indication will require 26 TEST subjects and 13 SOC control subjects assigned for a combined total of 78 randomized subjects.

#### Population:

Male and Female subjects suffering from chronic venous leg ulcers or diabetic foot ulcers

#### Eligibility Criteria Venous Leg Ulcer (VLU):

#### Inclusion Criteria:

- 1. Male or female 21-80 years of age
- 2. Participated in the informed consent process and signed study specific informed consent document
- Willing and able to comply with study procedures, including study visits and study dressing regimens
- 4. Confirmation of venous disease by non-invasive venous studies with either Doppler-confirmed venous reflux or having ≥ 2 clinical characteristics of venous insufficiency (varicose veins, lipodermatosclersosis, venous dermatitis, atrophie blanche, edema). Biopsy done to exclude other skin conditions e.g. cancer on ulcers ≥ 6 months
- 5. HbA1c of ≤ 10%
- 6. Have a venous ulcer between the knee and ankle, at or above the malleolus
- 7. Target wound size  $\geq 4 \text{ cm}^2$  to  $\leq 150 \text{ cm}^2$  in area without exposed tendon, muscle or bone
- 8. Target wound duration of at least 3 months and less than or equal to 12 months as of the date the subject signs consent for study
- 9. VLU may have characteristics that include yellow/white slough with or without fibrous/scar tissue and/or non-viable tissue, but not mandatory
- 10. Be willing and able (or have family member/friend willing and able) to apply required dressing changes as well as the ability of the subject to tolerate limb compression bandage

#### **Exclusion Criteria:**

- 1. Subjects with a BMI ≥ 65
- 2. Subject is medically unable to consent (due to head trauma, coma, etc.) or cognitively impaired (due to being mentally challenged, having Alzheimer's, etc.)
- 3. Subject is an active smoker
- 4. Subject has any history of fish allergy or a known sensitivity to any of the SOC materials which come into contact with the skin
- 5. Ankle-Branchial Index (ABI) less than 0.80 or greater than 1.3
- 6. Presence of any monophasic waveforms
- 7. Subject has the following abnormal lab values: Albumin < 2.5 g/dL; Total Protein < 5 g/dL; BUN above 25 mg/dL; Creatinine > 3.0 mg/dL
- 8. Any active cancer other than a nonmelanoma skin cancer; any previous cancer must be in remission for at least 1 year; bone cancer or metastatic disease of the affected limb, radiation therapy to the foot, or has had chemotherapy within the last 12 months

9. Suspicion of malignancy within VLU. Any wound that has been present for ≥ 6 months and hasn't previously been biopsied, a biopsy must be performed. Also, if a clinical suspicion of malignancy exists in the opinion of the Investigator, a biopsy should be performed regardless of duration of wound

- 10. Life expectancy < 6 months
- 11. Subject has received within 28 days of screening a treatment which is known to interfere with or affect the rate and quality of wound healing (e.g., thrombolysis, systemic steroids, immunosuppressive therapy, autoimmune disease therapy, dialysis, radiation therapy, chemotherapy) to the leg or who may receive such medications during the screening period or who are anticipated to require such medications during the course of the study.
- 12. History of immunodeficiency or any illness or condition that could interfere with wound healing e.g., lymphedema, end-stage renal disease, severe malnutrition, liver disease, aplastic anemia, Raynaud's Syndrome, connective tissue disorder, acquired immune deficiency syndrome, HIV positive, or sickle cell anemia
- 13. Ulcers due to non-venous etiology and leg ulcers associated with mixed etiology
- 14. Untreated osteomyelitis
- 15. Hepatitis
- 16. Acute deep venous thrombosis
- 17. Allergy to lidocaine and/or epinephrine
- 18. Subject's inability to successfully tolerate compression therapy that is changed weekly
- 19. Suspected or confirmed gangrene or wound infection of the study ulcer, as evidenced by tissue necrosis, redness, pain, and/or purulent drainage and/or receiving systemic antibiotics for the treatment of such
- 20. Target wound has received hyperbaric therapy or wound dressings that include growth factors, engineered tissues, or skin substitutes within 28 days of randomization or is scheduled to receive treatment during the study e.g., Apligraf, PriMatrix, AMNIOEXCEL (first generation), Regranex, Dermagraft, EpiFix, GraftJacket, OASIS, Omnigraft, or Integra BMWD

\_\_\_\_\_

